#### 4.2.5. Analyses of secondary outcomes at patient level

For all secondary outcomes at the individual level, we will fit the Equation (1) using generalized linear mixed models to accommodate each secondary outcome (e.g., logistic mixed model for mortality; Poisson/negative-binomial for rates, etc.). We will adjust for the same covariates, except when it is not possible because of the outcome type. For instance, ventilator associated events can be measured only in patients with invasive mechanical ventilation.

For the secondary outcomes that involve rates or patient-days, catheter-days and etc., we will include all patients who fulfilled all inclusion criteria and none exclusion criteria, and we will include readmissions.

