## 2.4. Randomization and masking

After a 2-month observation period (baseline period) in which performance indicators for eligible ICUs were collected without any intervention (with the purpose of obtaining data for randomization, analysis and characterization of the initial ICU status), the ICUs eligible for the study were randomized. The 30 ICUs were randomly assigned to either the intervention group (n=15) or the control group (n=15) using a restricted randomization algorithm that minimizes imbalance between treatment groups across the following baseline covariates at the ICU level:

- 1) number of ICU beds

- 2) mean SAPS 3, in points
- 3) mean ICU length of stay (LOS), in days
- 4) Standardized mortality rate (SMR)
- 5) Standardized resource use (SRU), and
- 6) A two-category dummy indicator for Brazilian region where the ICU is located (regions South and Southeast x regions North/Northeast/Central-West).

We followed all the steps recommended by Carter and Hood during the application of the minimization algorithm. The randomization was performed at three times, including 14 units during the first randomization, followed by 7 and 9 units (Figure 1). We decided a priori to randomize at three times and the number of units at each randomization was pragmatic, allowing for ethical approval and completion of the baseline period, respecting the minimum of eight units during first randomization and minimum of six on subsequent randomizations.

For the first randomization, we followed the steps: 1) the database with the baseline data (2 months) were locked, 2) derivation of the six covariates per unit, 3) run the algorithm, generating the potential combinations of unit's allocation, 4) a random combination of allocations was selected. The order of each unit in the database was randomly sorted before the algorithm, as well as the order of potential allocations. The select allocation was coded as 0 and 1 by the algorithm. To select whether intervention would be 0 or 1, we performed the final simple randomization and 0 was allocated to the intervention arm. For the second and third blocks, we followed the same steps: we entered the baseline data of the previous block with its allocation and the new covariates. The algorithm accounts for the previous block covariates to calculate the new balance between

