#### 4.1.3. Missing data

We will perform multiple imputation if missing data on core variables is >5%, under the assumption that the missingness pattern is missing at random (MAR) conditional on the observed data. Core variables are defined as the covariates to be used in the main analysis of the primary outcome: SAPS-3 score, type of ICU admission, invasive mechanical

ventilation at ICU admission, number of ICU beds in the baseline, Brazilian region where the ICU is located, ICU performance in the baseline and order of randomization. We will follow the recommended and standard steps for multiple imputation. We will include the outcome and account for the clustered structure of the data. The imputation model will have the covariates used in the main model and auxiliary variables. We will start with 20 imputed datasets and change the number of imputed datasets based on the fraction of missing information (MFI). We will pool the estimates using Rubin's rules. The random number seed will be set to 2605.

For the severity scores, SAPS 3 and SOFA, we will consider “zero points” or “normal values” where data are missing. In case we perform multiple imputation, we will impute the final composite score.

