##### 4.2.1. Analysis of the primary outcome

The linear mixed model for the primary outcome will be the following:

$$Y_{ijk} = \beta_0 + \beta_1 X_{ij} + \beta_2 j + \beta_3 Z_{ijk} + \beta_4 L_{ij} + \mu_i + \nu_{ij} + \epsilon_{ijk} \quad \text{Equation (1)}$$

for cluster  $i$ , time-period  $j$  and participant  $k$ , where  $X_i$  denotes the trial arm for cluster  $i$  (coded 0 or 1), and  $j$  denotes the time-period in which participant  $k$  in cluster  $i$  is assessed (0 for baseline, 1 for after randomization). The individual error term is assumed to be Normally distributed and independent of  $\nu_{ij}$  and  $\mu_i$ . Random terms are assumed to be Normally distributed, and  $\nu_{ij}$  is assumed independent of  $\mu_i$ .  $Z_{ijk}$  and  $L_{ij}$  are the matrix of covariates at the individual level and unit level, respectively.  $\beta_1$  is the coefficient of interest for the trial, i.e., the estimate for the difference between those receiving the intervention and those in the control group.

For the primary outcome, we will include the index admission of a patient, i.e., we will not include ICU readmissions. The primary outcome – ICU LOS – will be log-transformed to account for the normality of the residuals of the linear mixed model. These two steps (not including readmissions and log-transformation) were used for the power calculations.

We will use the identity link in the model for the primary outcome and the Satterthwaite's degree-of-freedom correction.

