##### *4.2.3.1. Readiness for discharge*

The primary outcome – ICU LOS – is an outcome that depends also on factors outside the ICU for those that improved during the ICU stay, such as ward bed availability. For this reason, we specified to also measure the ICU LOS in terms of readiness for discharge, i.e., days from ICU admission to the first day the attending team defined the patient was ready to be discharged alive. This variable was measured during the daily collection data and will be measured as counts, because we will not have time accuracy for its measurement. The attending clinicians were not aware that this would be an outcome of the TELESCOPE trial. We will fit the Equation (1) using generalized linear mixed models to accommodate it using a Poisson or negative-binomial family with a log link.

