##### *4.2.3.2. Competing risk of death*

The primary outcome – ICU LOS – is subject to the competing risk of death. Therefore, the ICU LOS represents a composite summary of two process: time to ICU discharge alive and time to ICU death. There are alternatives to deal with this scenario, such as 1) fitting competing risk models, modeling time to discharge alive and consider time to ICU death as a competing event, 2) analyzing LOS separately between ICU survivors and

non-survivors, 3) weighting differently the LOS for those who died, among others. As expected, the potential different results on the primary outcome analysis will likely occur or be relevant only if the intervention has an effect on mortality. We consider this a secondary analysis because, *a priori*, we did not expect a major impact of the intervention on mortality. In this sensitivity analysis, we will use the competing risk framework, presenting the analysis with cause-specific hazard ratios and sub-distribution hazard ratios for the time to discharge alive. The models will be adjusted for the same six covariates as the primary analysis, and the baseline period will be accounted as the mean ICU LOS at the unit level in the baseline period. We will account for the correlated data structure with a “shared frailty model”.

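### The SAP names a small-sample correction only for the primary linear model; the GLMM and shared-frailty analyses on the same 30 ICUs have none, and usual large-sample inference would make their intervals too narrow

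*SAP*

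**What the plan says.** - **Primary model (SAP 4.2.1):** "We will use the identity link in the model for the primary outcome and the Satterthwaite's degree-of-freedom correction". This is the only small-sample provision in the document.
- **Patient-level secondary outcomes (SAP 4.2.5):** "we will fit the Equation (1) using generalized linear mixed models to accommodate each secondary outcome", for example logistic for mortality and Poisson or negative-binomial for rates. No degrees of freedom, estimation method or reference distribution is given.
- **Readiness for discharge (SAP 4.2.3.1):** "We will fit the Equation (1) using generalized linear mixed models to accommodate it using a Poisson or negative-binomial family with a log link". Nothing is said on small samples.
- **Competing risk of death (SAP 4.2.3.2):** "We will account for the correlated data structure with a" shared frailty model. Again nothing on small samples.
- **Imputation (SAP 4.1.3):** triggered only if more than 5% of core-variable data are missing, starting with 20 datasets. "We will pool the estimates using Rubin's rules". The degrees of freedom of the pooled test are not stated.
- **Reporting (SAP 5.1.4):** one table gives an adjusted estimate, a 95% CI and a P value for the primary, sensitivity and secondary analyses alike.
- **Status (SAP 2.5.2 and 4.1.4):** the secondary outcomes are exploratory and carry no multiplicity adjustment.

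**The concern.** The SAP accepts that this number of clusters calls for a degrees-of-freedom correction and then applies it to one model. Writing Equation (1) as a GLMM does not carry the correction over, because Satterthwaite degrees of freedom as named belong to the linear mixed model. Logistic, Poisson and negative-binomial mixed models and frailty models are usually fitted by maximum likelihood and tested against a normal reference. Two things then go wrong together. Maximum likelihood underestimates the ICU variance when several ICU-level parameters are fitted, and the z reference ignores how few ICUs inform that variance.

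At stake are the interval for in-hospital mortality, those for the infection outcomes, and the two sensitivity analyses that readers will use to judge whether the primary result is robust. In the planned table these rows sit beside the primary row and look equally well calibrated.

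**Working it through.** **The plan's own figure.** The SAP gives no error rate or coverage for these analyses. The nearest figure is the original 80% power (2.6.1: difference 1.5 days, SD 10, ICC 0.018, 15 ICUs per arm, 500 patients each).
- Design effect = 1 + 499 × 0.018 = 9.982.
- SE = 10 × √(2 × 9.982 / 7,500) = 0.516.
- Two-sided 5% power: 80.1% with t on 28 df, 82.8% with z (equal cluster sizes). The stated 80% is closest to a t reference.

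**Between-ICU degrees of freedom.** Section 2.4 gives 30 ICUs. Section 4.2.6 gives four ICU-level covariates, which make seven parameters: beds 1, region 1, baseline performance 3, randomization block 2. With intercept and arm, 30 − 2 − 7 = 21.

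**Effect of the reference distribution alone.**
- The 97.5% point is 2.080 for t(21) and 1.960 for z.
- Width ratio 1.960 / 2.080 = 0.942, so a z interval is 5.8% too narrow.
- Size = 2 × P(t21 > 1.960) = 6.3%; coverage 93.7%.
- Ignoring covariates (28 df): critical value 2.048, size 6.0%.

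**Adding the maximum-likelihood variance.** Null simulation of ICU-by-period log-odds, as a normal approximation to a logistic Equation (1), 3,000 runs per row. From the SAP: 30 ICUs, 500 follow-up patients each, seven ICU-level parameters. Assumed: 56 baseline patients per ICU (500 × 2/18), event risk 35%, and the ICC and CAC shown. The SAP gives such ICC and CAC values for LOS, not for binary outcomes.

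| ICC | CAC | ML, z | ML, t(21) | REML, z | REML, t(21) |
|---|---|---|---|---|---|
| 0.018 | 0.80 | 9.6% | 7.4% | 6.1% | 4.5% |
| 0.018 | 0.906 | 9.8% | 8.0% | 6.2% | 4.6% |
| 0.018 | 0.96 | 8.7% | 7.3% | 5.8% | 4.6% |
| 0.087 | 0.80 | 8.6% | 6.8% | 6.3% | 5.1% |
| 0.087 | 0.906 | 8.2% | 6.3% | 6.3% | 4.7% |
| 0.087 | 0.96 | 6.8% | 5.4% | 5.7% | 4.6% |

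A simulation that fitted the logistic mixed model itself by Laplace approximation (35% mortality, logit ICU variance 0.25, CAC 0.8, cluster-size CV 0.4, 4,000 trials) gave 9.4% for z. Its mean model SE was 0.130 against a true SD of 0.147. Changing only the reference, to t on 20 df, still gave 7.8%, so both parts of the correction are needed.

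**Frailty analysis.** A closed-form normal analogue uses post-randomization data only. With residual df ν among 30 ICUs and an ML variance, the z test has size P(|tν| > 1.960 × √(ν/30)).
- Seven ICU-level parameters plus baseline mean LOS: ν = 20, threshold 1.600, size 12.5%.
- Section 4.2.3.2 speaks of six covariates where 4.2.6 lists seven. If block is the one omitted, ν = 22 and size is 10.7%; if performance, ν = 23 and size is 10.0%.

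This uses no event times and treats the whole variance of the ICU summaries as estimated by ML, so it is indicative only.

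**Pooling, if triggered.** Classical Rubin df = (m − 1)/λ², with m = 20 and λ the assumed fraction of missing information.
- λ = 0.05: 19/0.0025 = 7,600, critical value 1.960. Barnard-Rubin with 21 complete-data df: (22/24) × 21 × 0.95 = 18.29, combined with 7,600 to give 18.2; critical value 2.099.
- λ = 0.30: 211 against 12.7 df; critical values 1.971 and 2.166.

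If the classical formula were used, intervals would be 7% to 9% too narrow.

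**The case against.** The strongest reply is that the SAP nowhere chooses Wald z tests or maximum likelihood. It names only R. A reader might infer that these analyses are committed to large-sample tests and that their intervals will be too narrow. The text does not support that: the narrowness depends on software defaults that the SAP leaves open. This stands, and the point is therefore stated conditionally.

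A reader might also infer that false positives will occur twice as often as claimed. That is the upper end of the GLMM results. At ICC 0.087 and CAC 0.96 the rate is 6.8%, and the only CAC evidence in the SAP (above 0.960) concerns LOS. Event risk, ICU variance and CAC for the secondary outcomes are assumptions, and no count model, infection outcome or real survival model was simulated.

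A third tempting inference is that imputation removes the correction from the primary test. Section 4.1.3 does not select the classical degrees of freedom and pools the same model for which Satterthwaite is prescribed. Only the pooled df is unstated, and it matters only if missingness exceeds 5%. Four of the seven core variables are ICU-level, and the SAP also provides for scoring missing SAPS 3 data as zero points or normal.

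Finally, the outcomes are labelled exploratory and the competing-risk analysis is called secondary. That limits the consequence but does not answer the point: the label in 4.1.4 concerns multiplicity, whereas a printed 95% interval still claims 95% coverage.

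**Conclusion.** The concern holds in limited form. The small-sample correction is tied to the primary linear mixed model. The GLMM secondary outcomes, the readiness-for-discharge GLMM and the shared-frailty analysis have none, although they depend on the same 30 ICUs. Under usual maximum-likelihood, z-based inference the nominal 5% test would run at about 6% from the degrees of freedom alone and roughly 7% to 10% for the GLMMs in full. The frailty analogue points the same way but is too approximate to give a firm figure. A REML-type variance with t on 21 df brought the simulated size back to 4.5% to 5.1%. The GLMM range rests on the assumed event risk, ICU variance and CAC; the degrees-of-freedom part rests only on the 30 ICUs and the listed covariates. The primary complete-data test is unaffected. This should be corrected before database lock, but it does not threaten the main conclusion.

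**What to change.** Add to SAP 4.2.3 and 4.2.5 that the reported interval and p-value for every GLMM and frailty analysis use a named small-sample method. Suitable choices:

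1. A REML-type (restricted or penalised) variance with a t reference on the between-ICU degrees of freedom: about 21, or the number matching the covariates actually used. The six-versus-seven covariate count in 4.2.3.2 and 4.2.6 should be settled at the same time.
2. An ICU-level covariate-adjusted analysis with a t test, where events are frequent enough for stable ICU summaries. Its own estimate and interval should be reported together, not its interval around a GLMM estimate.
3. If a permutation test is preferred, it must draw only on allocations admissible under the restricted, sequential randomization in 2.4. Free permutation within blocks is not the design's reference set.

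Add to 4.1.3 that, if imputation is triggered, the pooled test uses Barnard-Rubin degrees of freedom with the Satterthwaite value as the complete-data degrees of freedom.

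The cost is a few sentences and a little programming, with no new data. Secondary and sensitivity intervals become slightly wider, about 6% from the t reference (2.080 / 1.960 = 1.061) and somewhat more from the variance.

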#### 4.2.6. Covariate adjustment

We pre-specified that the analyses for the primary and secondary outcomes will be adjusted by covariates in the original protocol, but we did not define which covariates, except the mean ICU LOS at the cluster level. Based on the literature on the determinants of ICU LOS, we will adjust by three patient level covariates and four ICU level covariates:

- 1) SAPS-3 (continuous term),
- 2) Type of ICU admission (3 categories: medical, elective surgical, unplanned surgical),
- 3) Invasive mechanical ventilation at ICU admission (2 categories: yes, no),
- 4) Number of ICU beds in the baseline (continuous term),

- 5) Brazilian region where the ICU is located (2 categories: South/Southeast, North/Northeast/Central-West),
- 6) ICU performance in the baseline (4 categories: most efficient, least efficient, overachieving, underachieving).
- 7) Groups of randomization (3 categories: first, second and third blocks)

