arms. We applied the same random sorting of order and potential unit allocations. The meaning of 0 and 1 was kept the same as the first block randomization (i.e., 0 to intervention and 1 to control) because it must follow the first block ascertainment. To ensure allocation concealment, all units were enrolled prior to randomization and the Ethics approval and the ICU and hospital coordinators signed the agreement with commitment to the trial; the statistician responsible for the randomization list received only the ICU identifier code, unaware of which unit it referred to; the allocation list was sent to the study coordinator, who informed simultaneously the ICUs about the randomization and allocation.

The allocations were done after the completion of the baseline, on 05 August 2019, 16 October 2019, and 29 January 2020, using the software R (v. 3.5.2).

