## 2.6. Power calculation

### 2.6.1. Original power calculation

Prior to the start of the trial and baseline period, for the funding application, we estimated a mean ICU length-of-stay of 8 [standard deviation (SD) 10] days for general adult public ICUs in Brazil. We used data from published literature and reports from the online project “UTIs Brasileiras”. In 2018, the “UTIs Brasileiras” dashboard had data of ICU LOS from 242 public ICUs in Brazil (n=3,199 beds). Using data from 20 ICUs (10 ICUs from [name] et al, 10 ICUs from the ORCHESTRA study, available in the *ems* R package), we estimated an intraclass correlation coefficient (ICC) of 0.018. Considering a two-arm cluster trial with an ICC of 0.018, for a minimum difference of an average length of stay of 1.5 days (8.0 to 6.5 days)

and SD of 10 days, power 80%, alpha 5%, we would need a total of 30 clusters (15 intervention units and 15 control units) with an average cluster size of 500 patients per ICU over a period of 18 months. Cluster size can vary and if the cluster size variation is high, usually measured by the coefficient of variation (CV), the power of the trial decreases. We estimated the CV using the expected minimum and maximum method of the cluster size: assuming a minimum cluster size of 350 patients and maximum of 650 patients (i.e., range 300, approximated SD of 75), for a mean size of 500 patients, we would have an approximated CV of 0.15 and maintain 80% power.

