period ICC. Considering a cluster parallel trial with baseline measure, with cross-sectional sampling structure, a correlation structure of a two-period decay, a coefficient of variation of clusters size of 0.4 (taken from the baseline period), we would maintain 80% power until a CAC value of  $\geq 0.906$ , without considering covariate-adjustment. We estimated the CAC on the 20 ICUs used for the estimation of initial ICC, using follow-up periods similar to the TELESCOPE trial, and in all occasions it was higher than 0.960. Considering the dynamic of ICU LOS and its high correlation overtime, we expect CAC to be high. Two issues that could reduce the power must be taken into account: 1) this new power calculation assumes that ICUs would have the same number of patients recruited in the baseline and post-randomization period (n=500); 2) equal number of ICUs randomized to intervention and control at each block, which occurred in the first block, but not for the second and third block. However, these estimations did not account for the covariate adjustment in the main model, also pre-specified in the original protocol, which decrease the ICC and increase precision by reducing the between-center variance and that we will adjust for randomization block in the analysis. Based on this scenario, after a meeting with an external advisory board on 05/10/2020, the steering committee decided to keep the original sample size and power calculation, conditioning it to updating the analysis plan in order to keep the covariate adjustment and to account for the baseline period.

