#### 4.1.5. Other issues

We will not compare baseline characteristics between treatment groups with Null hypothesis significance testing (NHST).

We will evaluate the calibration for in-hospital mortality of the SAPS3 score with data from the baseline period. If necessary, we will recalibrate the model for the studied population. All analyses will be performed with program R (3.4.1 version, the version will be updated at the time of analysis).

The TELESCOPE trial has been running during the COVID-19 pandemic. It is likely that the pandemic changed the usual characteristics of the admitted patients, both if an ICU from the TELESCOPE trial becomes a reference for COVID-19 patients or for non-COVID-19 patients. The ICU performance, both at control and intervention arms, could have influenced the decision-makers at the Federal, State and Municipal level to decide on referring an ICU to be COVID-19 or not. As ICU performance is, in this case, post-randomization, we will not adjust for whether an ICU is reference for COVID-19 or not in the analysis, otherwise it will break the randomization. Neither the steering committee nor tele-intensivists were responsible for any decision about an ICU being a reference or not to COVID-19.

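### Randomization block enters Equation (1) only as a time-constant covariate, so block-specific change across staggered calendar windows goes into the cluster-by-period variance and makes the standard error of the treatment effect somewhat conservative

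*SAP*

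**What the plan says.** - **Model.** SAP 4.2.1, Equation (1), has one fixed two-level period term (baseline, after randomization) common to all ICUs, a random ICU effect and a random ICU-by-period effect. SAP 4.2 explains that the last term lets secular trends differ at random between ICUs.
- **Block.** SAP 4.2.6 lists block as the seventh covariate: "Groups of randomization (3 categories: first, second and third blocks". No product of block with period is given. Calendar time appears only as an exploratory subgroup (4.2.7).
- **Timing.** SAP 2.4: blocks of 14, 7 and 9 ICUs were allocated "on 05 August 2019, 16 October 2019, and 29 January 2020". Figure 1 shows a common end of enrollment in April 2021 and baseline months running from June-July 2019 in block 1 to late 2019 in block 3.
- **Allocation.** SAP 2.6.2 assumed equal arms per block, "which occurred in the first block, but not for the second and third block". It names adjustment for block, with other covariate adjustment, among the things that offset possible loss of power.
- **Pandemic.** SAP 4.1.5: "The TELESCOPE trial has been running during the COVID-19 pandemic". It expects the case mix to have changed and declines to adjust for COVID-19 reference status because that arises after randomization.
- **Competing risks.** SAP 4.2.3.2: "The models will be adjusted for the same six covariates as the primary analysis". Section 4.2.6 lists three patient-level and four ICU-level covariates, which makes seven.

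**The concern.** The before/after contrast does not mean the same thing in the three blocks. Block 1 has several months of follow-up before the pandemic, and block 3 has almost none. If the pandemic or the season changed length of stay, the average change from baseline differs by block for reasons unrelated to treatment.

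A block main effect moves an ICU's baseline and follow-up by the same amount. The SAP expects a high cluster autocorrelation (CAC), under which the treatment effect is estimated mostly from within-ICU change, and there the block term largely drops out. It does not adjust the change by block, although 2.6.2 counts block adjustment among its offsets to lost power. The unexplained differences between blocks are read as random ICU-by-period variation. That lowers the effective CAC on which the 80% power statement depends and widens the interval for the treatment effect.

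**Working it through.** **1. The plan's own power figures.** Inputs from 2.6.1: the ICC, "we estimated an intraclass correlation coefficient (ICC) of 0.018"; a target effect of 1.5 days; an SD of 10; 5% alpha; 15 ICUs of 500 patients per arm. A two-sided test is assumed.
- Design effect = 1 + 499 × 0.018 = 9.982.
- SE = 10 × √(2 × 9.982 / 7,500) = 0.516 days.
- Power = 0.828 (normal) or 0.801 (t, 28 df). This reproduces 80%.

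Re-estimate in 2.6.2 (ICC 0.087, CAC 0.906, CV 0.4, 500 patients in each period), by generalized least squares with t on 28 df: power 0.814 with SD 10 and 0.830 with SD 9.8. This is close to the stated 80%.

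**2. Pandemic exposure by block.** Assumptions: pandemic from 1 March 2020, enrollment to 1 April 2021, even admissions.

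| Block | ICUs | Follow-up days | Days before March 2020 | Pandemic share |
|---|---|---|---|---|
| 1 | 14 | 605 | 209 (35%) | 0.655 |
| 2 | 7 | 533 | 137 (26%) | 0.743 |
| 3 | 9 | 428 | 32 (7%) | 0.925 |

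If the pandemic changes mean stay by D, the period shifts are 0.655D, 0.743D and 0.925D. Weighted by 14/30, 7/30 and 9/30, their between-ICU SD is 0.116D.

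**3. Effect on the standard error.** Variance of an ICU's change: V = σ²[2 × ICC × (1 − CAC) + (1 − ICC)(1/m₀ + 1/m₁)]. SE ratio = √(1 + (0.116D)²/V).

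On the log scale of the planned analysis, take σ = 1 (assumed; a lognormal with mean 7.8 and SD 9.8 has log SD √ln(1 + (9.8/7.8)²) = 0.97). Take m₁ = 500 and m₀ = 56, because two months at 500 patients per 18 months is 500 × 2/18.
- CAC 0.96: V = 0.00696 + 0.01813 = 0.0251.
- CAC 0.906: V = 0.01636 + 0.01813 = 0.0345.

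| D (log) | Rise in stay | Excess SE, CAC 0.96 | Excess SE, CAC 0.906 |
|---|---|---|---|
| 0.2 | 22% | 1.1% | 0.8% |
| 0.3 | 35% | 2.4% | 1.7% |
| 0.5 | 65% | 6.5% | 4.8% |
| 0.7 | 101% | 12.4% | 9.1% |

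As a reduction in SE from adding block-by-period, 6.5% is 1 − 1/1.065 = 6% and 12.4% is 11%. Mixed-model simulations agree: about 1-6% for D of 0.3 to 0.5.

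In days, a change of 4 days with m₀ = 56 gives 3.2% (CAC 0.906) to 4.4% (CAC 0.96). With the 500 baseline patients assumed in 2.6.2, it gives 5.4% to 10.0%. Two months of baseline are unlikely to supply 500 patients, and 2.6.2 itself flags that assumption.

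**4. Simulation of Equation (1)** on cluster-period means, in days, with splits such as 7:7, 4:3, 4:5 (assumed):
- No shift, CAC 0.906, 500 per period: mean SE 0.486 with the main effect and 0.489 with block-by-period, a cost of 0.6%.
- 4-day pandemic change, CAC 0.96, 500 per period, no treatment effect: mean SE 0.395 against 0.360. The empirical SD of the estimate hardly moves (0.360 against 0.362). Type I error is 0.023 against 0.040.
- Same change with 56 baseline patients: mean SE 0.563 against 0.542, type I error 0.040 against 0.042.
- Arbitrary shifts of 0, 1 and 2 days, CAC 0.96, 500 per period: mean SE 0.474 against 0.362, type I error 0.009 against 0.050. These shifts are not derived from anything in the SAP.

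**5. Bias.** Blocks 2 and 3 have odd numbers of ICUs (7 and 9), so their arms cannot be equal. With splits 4:3 and 4:5, the imbalance is (0.743 − 0.925)D/15 = −0.012D. With 5:2 and 3:6 it is three times that, −0.036D. For D = 4 days this is 0.05 to 0.15 days, against an SE of about 0.56 with 56 baseline patients.

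**The case against.** The strongest reply is that the plan already handles diverging trends. The random ICU-by-period term was included for that purpose, it absorbs block-specific shifts, and it keeps the test valid. This stands: across the simulated settings, type I error with the main effect alone ran from 0.009 to 0.056.

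It is also fair that SAPS 3, admission type and ventilation at admission may take up part of the pandemic change in case mix, which the calculations leave out. And 2.6.2 mentions block together with other covariates, so it does not rest the power claim on block alone.

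Two stronger readings are tempting and not supported:
- **That the pandemic confounds the treatment effect through the unequal blocks.** The SAP does not give the splits. Under near-equal splits the bias is about a tenth of a standard error or less.
- **That the trial forfeits a tenth or more of its precision.** Log shifts of 0, 0.1 and 0.2 across blocks do give a reported SE about 10-12% narrower with the interaction. But the exposures differ by only 0.925 − 0.655 = 0.271, so pandemic exposure alone would need D = 0.2/0.271 = 0.74, a rise of about 110% in stay. Even then the comparison is between reported standard errors. The true SD of the estimate went from 0.0544 to 0.0523, about 4%.

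What remains is that the fixed block term, as written, does not adjust the quantity that drives the estimate, and that a term which does so costs almost nothing.

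**Conclusion.** The point holds as a matter of efficiency and correct interval width, not of validity. Equation (1) does not adjust the before/after change by block, although the blocks' windows cover different calendar time. From pandemic exposure alone, the reported standard error is about 0-6% too wide for a rise in length of stay of up to about 65%. It is about 10% too wide only if stay doubles or blocks also shift for other reasons, such as the season of the baseline months. The true precision of the estimate changes little.

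These sizes assume a March 2020 start, even admissions, log SD 1, CAC between 0.906 and 0.96, about 56 baseline patients per ICU, and no help from patient covariates. The SAP gives neither the pandemic shift nor the within-block splits. More baseline patients would make the loss larger.

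The mismatch between six and seven covariates is a separate, definite inconsistency. It leaves open whether block is in the competing-risk model.

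**What to change.** - **4.2.1 and 4.2.6:** add the block-by-period interaction to Equation (1), and carry it into the generalized linear mixed models of 4.2.3.1 and 4.2.5 that reuse it. It takes 2 df (about 28 to 26) and costs under 1% in standard error if blocks do not differ. Block is fixed at randomization, so the reason in 4.1.5 for not adjusting for COVID-19 reference status does not apply. The SAP states that no analysis has yet been done, so the term can still be pre-specified.
- **4.2.3.2:** reconcile the count of six with the seven covariates in 4.2.6, so that block is clearly included. Baseline enters that model as the unit's mean length of stay, so the comparison is post-randomization only and a block main effect is enough.

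Both are wording changes and need no new data.
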